9.3 Primary Analysis Methods

The primary efficacy outcome measure is a binary measure of treatment failure/success as determined at 6-month time intervals post-intervention. Surgical failure rates will be compared graphically across the two treatment arms with Kaplan-Meier type plots, with survival curves computed using the product-limit estimator appropriately extended for interval estimation. While the original protocol indicated that a log-rank test would be use for the primary analysis, additional data that have come to light since the development of the protocol led to a masked decision to modify the primary analysis approach as specified in detail below.

This analysis contained several limitations that became apparent upon the studies initiation that makes revision necessary. First, the survival analysis methods initially proposed were developed for right censored data, while the outcome data for the bulge symptoms and anatomic failure is collected at the six 6-month follow-up visits, making the data a combination of interval censored and right censored. Second, results from long term follow-up of the OPTIMAL trial showed that the proportional hazards assumption is not likely hold over the 60-month follow-up time. Third, recent research has shown that it's possible for patients with uterovaginal prolapse to move in and out of "treatment failure" as defined above, such that these repeated failures are ignored in the defined analysis. The analysis proposed are selected to address these limitations.

The first two sections below describe a modified analytic approach that treat participants in a manner consistent with the original analysis design in that study participants that meet the criteria for treatment failure a remain treatment failures until they are lost to follow-up or the study ends. The proposed model-based and nonparametric analytic methods address interval censoring and non-proportional hazards in the assessment of the study's primary hypothesis. The model-based approach will serve as the primary analytic method for testing the efficacy of the two strategies for uterovaginal prolapse as it can control for study design and potentially confounding variables, while the nonparametric method will serve a confirmatory role, particularly in the masked analysis as detailed below. The third section focuses on modeling recurrent events to better understand the impact of the interventions over time. The analytic methods for estimating survival curves will first be conducted in a blinded fashion on all subjects, ignoring treatment assignment as a part of a masked analysis, then comparing subjects randomized their interventions in an unmasked analysis.

Model-based analysis:

To appropriately account for the interval censored nature of the follow-up data, where the proportional hazards assumption is unlikely to hold, and control for study design and potentially confounding variables in assessing intervention effects, a piecewise exponential (PWE) survival model with mixed effects will be employed. The PWE survival model is a model in which the time scale is divided into K periods and the baseline hazard function, h(t), is assumed to be constant within each period such that $h(t) = \lambda_k \exp(\beta \mathbf{X})$, where λ_k is the hazard function for period k, **X** matrix of explanatory variables with vector β coefficients (Breslow 1974). This piecewise approach effectively eliminates the need to specify the distribution of the hazard function and satisfies the proportional hazards assumption if the baseline hazard is constant within each period. The PWE survival model has been shown to be equivalent to a Poisson regression model if the baseline hazard function is constant as a function of time [i.e. $h(t) = \lambda(t) = \lambda$] (Laird & Olivier, 1981). This means that the PWE survival model can be fitted with a generalized linear mixed model (GLMM) by taking survival data consisting of observed survival time t_i for the *i*-th subject with a treatment failure indicator d_i within the k-th period, so that t_{ik} denotes survival time and d_{ik} the occurrence of treatment failure for the *i*-th subject in period k, creating a number of pseudo-observations, one for each combination of subject and period. A PWE survival model can then be fit by handling treatment failure indicators as if they were Poisson observations with means $\mu_{ik} = \lambda_{ik} t_{ik}$, where λ_{ik} is the hazard for the *i*-th subject in period

k. Also needed is an offset variable denoting a logarithm of the time at risk during each period (Crowther et al., 2012). It is important to note that PWE survival models do not assume that the d_{ik} have independent Poisson distributions as a subject who has treatment failure in period k(i), must have had no failure in all prior periods. Rather, each *i*-th subject across period covariance is modeled as a random effect in the GLMM.

The GLMM of the PWE survival model will be is specified with (1) a Poisson distribution, (2) an offset variable denoting the logarithm of the exposure time during a given period, and (3) subjectspecific random intercepts to incorporate within-subject homogeneity, using the SAS GLIMMIX procedure in SAS STAT version 14.2 (SAS Institute Inc. 2016). The study's follow-up time will be divided into three periods: first, before and up to 12-months; second, 13 months to 30 months; and third, 31 months and beyond. The choice cut points will be evaluated during the masked analysis with a plot of the NPMLE survival function (described below) and adjusted if necessary. As it is possible for subjects to have a right censored treatment failure at the beginning of a period, resulting in an exposure time of zero and a offset variable that is undefined, subjects experiencing a treatment failure at the beginning of a given period will be assigned an exposure time of 0.5 months and an offset variable of log(0.5). The unmasked analysis will use the GLMM specified above to generate an overall test of the failure hazard ratio across the two interventions using a two-sided hypothesis test with an overall type I error rate of 0.05, controlling for the design variables of site the subject was recruited into. Also, the point and interval estimates of 12-, 24- and 36-month treatment failure rates on each intervention arm as well as hazard ratios between the two arms will be provided. Additional models will be used to evaluate potentially confounding variables of subject age and prior prolapse surgery.

Nonparametric analysis:

This analysis will employ nonparametric maximum likelihood estimation (NPMLE) to estimate survival functions in a similar manner as the Kaplan-Meier estimator for right censored data, but also employs a combination of the EM and iterative convex minorant (ICM) algorithms to estimate the survival function in non-overlapping intervals (Wellner and Zhan, 1997). Standard errors of the survival curves and the covariance matrix for the generalized rank statistic will be generated with the multiple imputation method developed by Sun (2001). The overall test for the difference in the two interventions survival curves will be conducted with the generalized log-rank test (Huang, Lee, and Yu, 2008). In addition, point estimates and 95% confidence limits will be estimated at 12-, 24- and 36-month intervals. The nonparametric survival analysis methods detailed above will be carried out using the ICLIFETEST procedure. The advantage of this approach is that it makes no assumptions about the distribution of the interval centered data and permits estimated survival curves to be non-monotonic (no proportional hazards assumption), although it is unable to adjust for study design and potential confounders. This analysis will primarily be used to confirm the results of the model-based analysis, particularly the specification of the piecewise survival function in the masked analysis.

Analysis of multiple treatment failures:

Data from other trials that emerged after this study was designed have shown that patients with uterovaginal prolapse can move in and out of the state of "treatment failure" after surgical repair, and that the standard survival methods employed above ignore these repeated events; as such the survival approach may underestimate the impact of the interventions in the treatment of uterovaginal prolapse. This concern is specifically relevant for the treatment failure criteria anatomic failure and reported bothersome vaginal bulge symptoms, which are measured repeatedly at each of the follow-ups while retreatment with surgery or pessary result in a permanent failure. Below are two analytic approaches that focus on answering two questions that may be of practical interest to clinicians: (1) is there a difference in the prevalence of subjects meeting failure criteria (anatomic failure, bothersome

symptoms or retreatment) at 12-, 24- and 36- month follow-up times between the interventions; and (2) is there a difference in the rates of anatomic failure and bothersome bulge symptoms over follow-up time between the two interventions.

For the first question, at 12-, 24- and 36-month follow-up times, the proportion of subjects meeting specific failure criteria (anatomic failure, bothersome bulge symptoms, retreatment, no failure) will be compared across intervention groups using the Fisher-Freeman-Halton's exact test for r x c tables as proportion of subjects receiving retreatment will likely be small (Lydersen et al. 2007). If a subject meets more than one failure criteria, she will be classified as follows: retreatment and any combination of anatomic failure and bothersome bulge symptoms will be classified as retreatment; no retreatment but both anatomic failure and bothersome bulge symptoms will be classified as anatomic failure. Additionally, within each follow-up time, the odds of subjects being classified as treatment failures at that follow-up time (not being retained as failures if they met failure criteria at an earlier follow-up) will be compared across treatment groups with logistic regression models that will control for site, age and prior prolapse surgery.

Rates of anatomic failure and bothersome bulge symptoms over the follow-up time will be modeled using a GLMM (a shared frailty model), fitted by Gaussian quadrature in SAS NLMIXED procedure, where a piecewise baseline hazard function will again be employed to generate a parametric model that eliminates the need to specify the distribution of the hazard function and satisfies the proportional hazards assumption if the baseline hazard is constant within each period (Liu & Huang, 2008). The model will be specified with a period indicator variable for each follow-up; variables for treatment failure and for the length of time in each follow-up period; study design (site) indicator variables; an intervention indicator; and as having a normal distribution for the subject random intercept.

Note that this model uses each 6-month follow-up interval as a period in the piecewise model. This is primarily to assure that within each period, there is only one treatment failure/success indicator. It is possible to combine multiple intervals into periods when treatment failure become sparse. This can be done in the masked analysis. The unmasked analysis will generate an overall test of the failure hazard ratio across the two interventions using a two-sided hypothesis test with an overall type I error rate of 0.05, controlling for the design variables of site the subject was recruited into. Also, the point and interval estimates of 12-, 24- and 36-month treatment failure rates on each intervention arm as well as hazard ratios between the two arms will be provided. Additional models will be used to evaluate potentially confounding variables of subject age and prior prolapse surgery.

All analyses will be implemented using SAS Version 9.3 or later.

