4.3 Study Arm Assignment and Randomization

After consent is obtained from the participant and eligibility is determined, the participant will be randomized to one of the two treatment arms using a phone-based randomization system after the participant is in the operating room. The patient will be randomized to one of two apical procedures: either a vaginal hysterectomy with USLS or mesh strap vaginal hysteropexy (UPHOLD procedure). Other native tissue vaginal wall prolapse repairs (e.g. anterior colporrhaphy, posterior colporrhaphy, perineorrhaphy) will be allowed as needed.

Randomization (1:1 to the two treatment arms) will be performed using permuted blocks, with a block size that is known only to the DCC and will be stratified by site.

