While the study is designed to demonstrate the superiority of either of the two treatment arms in comparison to the other, the comparison of the efficacy and safety outcomes for the two treatment arms has important public health implications even if a statistical difference in efficacy is not demonstrated. Consequently, the futility analyses will focus on failure to adequately enroll the study rather than on inability to show a difference in efficacy between the arms. The study is designed to enroll 180 participants over a 24 month period or 7.5 participants per month across the 8 participating sites. The DSMB will evaluate enrollment at 6-month intervals starting after the first site has achieved IRB approval. If at these 6-month reviews, the DSMB finds that the study is not enrolling at a rate of at least 5 participants per month (which would allow the study to enroll over a 3-year period) they will consider recommending stopping the study for futility.

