9 EFFICACY ANALYSES

9.1 Overview of Efficacy Analyses Methods

All efficacy analyses will be performed using the ITT population unless otherwise specified. All efficacy variables will be listed by subject within study center and assessment time. The data will be summarized by treatment group.

The primary efficacy outcome measure is a binary measure of treatment failure/success as determined at 6-month time intervals post-intervention, and the primary analytic approach will utilize a survival model to evaluate differences in time to treatment failure between the two treatment arms. Generally, all secondary efficacy variables will be collected longitudinally across this study at six-month. Consequently, secondary analyses will be conducted using appropriate models for these correlated data collected across time. Specifically, continuous outcome variables will be analyzed using linear mixed models and binary outcome variables will be analyzed using robust Poisson regression models with a log link. Most models will include terms for treatment, time, and the treatment by time interaction and for the stratification variables included in the study design (site). Additional details are provided in the specific sections below.

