9.4.2 Comparison of Anatomical Measures of Treatment Efficacy

One component of the first secondary efficacy aim is to compare anatomical measures of treatment efficacy across the two arms. For the 3 continuous measures (Ba, Bp, and C), the linear model described above will be used to generate mean estimates of each of these 3 metrics for the two treatment arms at each of the post-operative visits. For the binary measure of $C > \frac{1}{2}$ TLV, large-sample chi-square tests will be used to compare incidence at different time points.

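### The chi-square tests for apical position depart without explanation from the SAP's site-adjusted method for binary outcomes, and the statement that the confirmatory log-rank cannot adjust for design is too broad as regards site

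*SAP*

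**What the plan says.** **Randomisation.** Allocation is 1:1 in permuted blocks, "with a block size that is known only to the DCC and will be stratified by site" (SAP 4.3; Protocol H agrees). SAP 7.4 describes recruitment "across the 8 participating sites".

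**Apical position.** SAP 9.1 sets a general rule: "binary outcome variables will be analyzed using robust Poisson regression models with a log link". It adds that most models carry site. SAP 9.4.1 gives the detail: a GEE extension with treatment, visit, their interaction and site. The SAP 9.2 table lists C > -1/2 TVL as a binary secondary outcome at the 6-month visits. For this outcome SAP 9.4.2 states "large-sample chi-square tests will be used to compare incidence at different time points", without a reason.

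**Nonparametric analysis.** In SAP 9.3 the primary test is a piecewise exponential mixed model that controls for site. Beside it, in a confirmatory role, "The overall test for the difference in the two interventions survival curves will be conducted with the generalized log-rank test". The SAP credits this approach with few assumptions, "although it is unable to adjust for study design and potential confounders".

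**Failure categories.** Also in SAP 9.3, the failure categories at 12, 24 and 36 months "will be compared across intervention groups using the Fisher-Freeman-Halton's exact test for r x c tables". The reason given is that few retreatments are expected. Logistic models at the same visits adjust for site, age and prior prolapse surgery.

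**Elsewhere.** SAP 10.2 plans Cochran-Mantel-Haenszel (CMH) statistics stratified by site for binary and ordinal perioperative measures.

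**The concern.** With blocks inside each site, the arms are nearly balanced on site by design. Differences between sites then add almost nothing to the true variance of the treatment comparison. An unstratified test still counts them in its estimated variance. If sites differ in risk, that test is conservative and loses power.

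Two things are at stake. The first is the analysis of C > -1/2 TVL. Protocol B.2 calls change in point C an important secondary outcome with its own analysis plan. Yet the binary version gets a weaker method than the SAP's default: no site term, no use of the repeated measures, and separate tests. POPQ is scheduled at 6, 12, 18, 24, 30 and 36 months, so testing every visit would give six tests where SAP 9.4.1 offers one contrast over 36 months plus visit-specific estimates.

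The second is the reading of the confirmatory test. If the site-adjusted primary model and the unadjusted log-rank disagree, the reader cannot tell whether the cause is model form or site adjustment.

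**Working it through.** **1. The binary outcome, section against section.** SAP 9.1 and 9.4.1 make the site-adjusted, repeated-measures Poisson model the general approach. Protocol O also plans model-based analysis of binary secondary outcomes, to account for correlation between measures. SAP 9.4.2 drops site and the repeated structure and gives no reason.

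**2. Can a nonparametric test respect site?** For a log-rank statistic, within site s and over event times t:

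- U_s = Σ_t (d1 − d·n1/n)
- V_s = Σ_t d·(n1/n)(1 − n1/n)(n − d)/(n − 1)
- stratified test = (Σ_s U_s)² / Σ_s V_s

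Here d is failures, n is number at risk, and the suffix 1 marks one arm. The same summation gives the CMH test for a binary outcome. An interval-censored score and its variance can in principle be summed over sites in the same way.

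**3. The plan's own power figure.** Inputs (Protocol N): 80% against 90% success at 24 months, exponential failure, N = 180, 2-year accrual, 36 months after last enrolment, 5% loss per year.

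- Hazards per year: −ln(0.8)/2 = 0.1116 and −ln(0.9)/2 = 0.0527; ratio 0.472, as stated.
- Loss hazard η = −ln(0.95) = 0.0513.
- P(event) = λ/(λ+η) × {1 − [e^(−3(λ+η)) − e^(−5(λ+η))]/[2(λ+η)]} = 0.326 (native tissue) and 0.172 (mesh).
- Expected events: 90 × 0.326 + 90 × 0.172 ≈ 44.8, or 44.8/8 ≈ 5.6 per site.
- Schoenfeld power: √44.8/2 × |ln 0.472| − 1.96 = 2.51 − 1.96 = 0.55, giving 0.71.
- Freedman power: √44.8 × 0.528/1.472 − 1.96 = 2.40 − 1.96 = 0.44, giving 0.67.

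The stated power of 0.89 is not reproduced. That is a separate matter; it is shown here because it explains why the simulated power below starts near 0.67.

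**4. Simulation.** 3,000 trials per setting, N = 180, 8 sites, 6-monthly visits, two-sided 0.05. Assumed, because the documents do not give them: block size 4, moderately unequal site sizes, and the SD of log hazard between sites. Monte Carlo standard error is about 0.004 for size and 0.009 for power.

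| Site SD | | Log-rank, unstratified → stratified | 36-month chi-square → site-stratified CMH |
|---|---|---|---|
| 0 | size | 0.052 → 0.048 | 0.045 → 0.046 |
| 0.5 | size | 0.049 → 0.054 | 0.044 → 0.050 |
| 1.0 | size | 0.028 → 0.054 | 0.031 → 0.052 |
| 0 | power, HR 0.472 | 0.666 → 0.660 | 0.626 → 0.625 |
| 0.5 | power, HR 0.472 | 0.669 → 0.681 | 0.637 → 0.656 |
| 1.0 | power, HR 0.472 | 0.627 → 0.725 | 0.588 → 0.673 |

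At SD 1.0 the gain is 0.725 − 0.627 = 0.098 for the log-rank and 0.673 − 0.588 = 0.085 for the binary test. At SD 0.5 the gains are 0.012 and 0.019.

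**5. What these SDs mean.** Take 80% success at 24 months in a typical site's native tissue arm. Sites one SD better or worse then have success 0.8^exp(∓SD). For SD 0.5 this is 87% and 69%; for SD 1.0 it is 92% and 55%. The second spread is very large.

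**Limits.** The log-rank simulated is the right-censored form, standing in for the interval-censored test. The binary comparison uses failure by 36 months, standing in for C > -1/2 TVL, for which the documents give no expected rate.

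**The case against.** No binding rule is broken. SAP 7.6 requires centre only in model-based analyses, SAP 7.2 and 9.1 speak of most analyses or models, and SAP 9.4.1 says its approach applies generally. SAP 9.4.2 is a specific provision, and SAP 7.7 makes secondary p-values descriptive. All of this stands. It makes the chi-square an unexplained exception, not a violation.

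On the log-rank, the sentence is fair for age or prior surgery. Whether the named SAS procedure and its imputation-based covariance offer stratification cannot be settled from the documents. The analysis is also meant chiefly to check the piecewise form in masked data, where arms are ignored and site strata for an arm comparison are irrelevant. With fewer than six expected failures per site, a simple unstratified check beside an adjusted primary model is defensible. This stands too, and it is why a stratified version is proposed as an addition.

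A reader might infer that all three unstratified comparisons rest on the same mistaken ground. They do not. The inability to adjust is stated only for the nonparametric survival analysis. The exact test is justified by sparse retreatment and has a site-adjusted companion, and the chi-square has no stated ground.

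**Conclusion.** The point holds as a minor improvement. The chi-square plan for C > -1/2 TVL departs, unexplained, from the SAP's own method and ignores the randomisation strata. The wording on the confirmatory test is too broad for site.

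If sites are alike, nothing changes. At a site log-hazard SD of 0.5 the power difference is 1 to 2 points, at or little above simulation error. Clear conservatism (size about 0.03, power loss about 9 to 10 points) appears only at an assumed SD of 1.0. Those sizes come from the stand-in tests described above.

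Two stronger readings are not supported. One is a risk of false positives: unstratified size did not exceed nominal beyond simulation error in any setting. The other is that the primary test itself ignores site, because SAP 3.1.1 still names a log-rank test. SAP 9.3 explains that the approach was changed under masking and designates the site-adjusted model as primary. SAP 3.1.1 should be brought into line, but it does not make the unstratified test primary.

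**What to change.** 1. **SAP 9.4.2:** analyse C > -1/2 TVL with the SAP 9.4.1 robust Poisson GEE (treatment, visit, interaction, site), or with a site-stratified CMH test at each visit. Name the CMH test as the fallback if an arm has no positive cases at a visit, since the log-link effect is then not estimable. If the chi-square is kept, state why.
2. **SAP 9.3, nonparametric analysis:** add a site-stratified generalized log-rank, at least as a sensitivity analysis beside the unstratified test. Confirm first that the software supports it, or specify the summation by hand.
3. **Same paragraph:** limit the statement about being unable to adjust to general covariates.
4. **Exact failure-category test:** leave as it is. The site-adjusted logistic model at the same visits covers the gap, and permuting a sparse four-category table within sites is a debatable extra.

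The cost is SAP wording and minor programming. Sites with few failures will contribute little to the stratified tests, but stratifying cost less than one point of power in simulation when sites were alike.
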